5.1.3.2 Immunogenicity

All analyses will be descriptive; no hypotheses will be tested. Data will be summarized and presented for each age group.

The following immunogenicity parameters^a will be calculated for each influenza strain with 95% CIs:

- Geometric mean HAI assay titers at pre-vaccination and post-final vaccination
- Geometric means of titer ratios (post-final vaccination divided by pre-vaccination).
- Seroprotection rates: The percentages of subjects with a titer ≥ 40 (1/dil) at pre-vaccination and at post-final vaccination
- Seroconversion rates: The percentages of subjects with either a pre-vaccination titer < 10 (1/dil) and a post-final vaccination titer ≥ 40 (1/dil), or a pre-vaccination titer ≥ 10 (1/dil) and a ≥ 4 -fold increase in post-final vaccination titer

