
Statistical Methods:
	
Summaries of baseline demographic characteristics of the study subjects will be presented. The number of subjects enrolled and their age at enrollment (mean, median, and minimum and maximum), sex, race, and ethnic origin will be summarized, along with the number and description of protocol deviations.
 
For the main safety and immunogenicity parameters, 95% confidence intervals (CIs) of point estimates of proportions will be calculated using the normal approximation for quantitative data and the exact binomial distribution (Clopper-Pearson method) for proportions. All analyses will be descriptive; no hypotheses will be tested.
 
Safety
 
The Safety Analysis Set will be used for the safety analyses. Subjects will be analyzed according to the vaccine they actually received.

	
Immunogenicity
 
The immunogenicity analyses will be performed on both the Full Analysis Set and the Per-Protocol Analysis Set. Data will be summarized and presented for each group.
 
The following immunogenicity parameters^a will be calculated for each influenza strain with 95% CIs:
 
• Geometric mean HAI assay titers at pre-vaccination and post-final vaccination• Geometric means of titer ratios (post-final vaccination divided by pre-vaccination).• Seroprotection rates: The percentages of subjects with a titer ≥ 40 (1/dil) at pre-vaccination and at post-final vaccination• Seroconversion rates: The percentages of subjects with either a pre-vaccination titer < 10 (1/dil) and a post-final vaccination titer ≥ 40 (1/dil), or a pre-vaccination titer ≥ 10 (1/dil) and a ≥ 4-fold increase in post-final vaccination titer 
^a Post-final vaccination in each of the immunogenicity parameters is defined as 28 (window, 28–35) days post-final vaccination for subjects 6 months to < 9 years of age, and 21 (window, 21–28) days post-vaccination for subjects ≥ 18 years of age.

--	--

Tables of Study Procedures

Study Flow Chart for Subjects 6 Months to < 9 Years of Age: 2 or 3 Visits, 1 or 2 Vaccinations

Visit Number	All Subjects		Subjects Receiving 1 Dose of Influenza Vaccine	Subjects Receiving 2 Doses of Influenza Vaccine		
	Visit 1	Telephone Contact	Visit 2	Visit 2	Telephone Contact	Visit 3
Study Timelines	Day 0	Visit 1 + 8 days	Visit 1 + 28 days	Visit 1 + 28 days	Visit 2 + 8 days	Visit 2 + 28 days
Time Windows	--	+ 8 to 10 days	+ 28 to 35 days	+ 28 to 35 days	+ 8 to 10 days	+ 28 to 35 days

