6.6 Treatment Compliance

The following measures will ensure that the vaccine doses administered comply with those planned, and that any non-compliance is documented so that it can be accounted for in the data analyses:

- All vaccinations will be administered by qualified study personnel
- The person in charge of product management at the site will maintain accountability records of product delivery to the study site, product inventory at the site, dose(s) given to each subject, and the disposal of unused or wasted doses

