3.1 Trial Design

GRC90 is a Phase IV, multi-center, open-label study of a planned 240 subjects to describe the safety and immunogenicity of Fluzone Quadrivalent vaccine in children 6 months to < 9 years of age and adults 18 to < 65 years of age, Flublok Quadrivalent vaccine in adults 18 to < 65 years of age, and Fluzone High-Dose vaccine in adults \geq 65 years of age.

Using a pre-programmed interactive response technology (IRT) system, each subject will be assigned to a vaccine group based on the subject's age at the time of enrollment. An approximately equal number of subjects from each group will be enrolled at each site.

Using the IRT system, subjects 18 to < 65 years of age will be randomly assigned to either Group 3 or Group 4. Enrollment in Group 3 and Group 4 will be stratified by age into 2 subgroups at each site so that approximately 50% of subjects at each site will be 18 to < 50 years of age and approximately 50% of subjects at each site will be 50 to < 65 years of age, so that an equal proportion of subjects within each age subgroup will receive either Fluzone Quadrivalent or Flublok Quadrivalent vaccine. If necessary to achieve 50% overall enrollment of subjects 50 to < 65 years of age and assignment of Fluzone Quadrivalent and Flublok Quadrivalent vaccines in a 1:1 ratio within each age subgroup (i.e., 18 to < 50 years of age and 50 to < 65 years of age), individual sites will be permitted to deviate from these ratios.

- Group 1: Children 6 to < 36 months of age assigned to receive a 0.25-mL dose of Fluzone Quadrivalent vaccine (30 subjects planned)
- Group 2: Children 3 to < 9 years of age assigned to receive a 0.5-mL dose of Fluzone Quadrivalent vaccine (30 subjects planned)
- Group 3: Adults 18 to < 65 years of age assigned to receive a 0.5-mL dose of Fluzone Quadrivalent vaccine (60 subjects planned)
- Group 4: Adults 18 to < 65 years of age assigned to receive a 0.5-mL dose of Flublok Quadrivalent vaccine (60 subjects planned)
- Group 5: Adults \geq 65 years of age assigned to receive a 0.5-mL dose of Fluzone High-Dose vaccine (60 subjects planned)

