5.2.1 Safety Analysis Set

The SafAS is defined as those subjects who have received at least 1 dose of the study vaccine^b. Subjects will have their safety data analyzed after “any dose” according to the vaccine they actually received as the first dose. Safety analysis after each dose will be assessed in the subset of the SafAS having received that dose. Subjects will have their safety data analyzed after each vaccination according to the vaccine they actually received for that dose.

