5.2.2 Full Analysis Set

The FAS is defined as the subset of subjects who received at least 1 dose of the study vaccine and have a valid post-vaccination blood sample result for at least 1 strain.

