5.2.3 Per-Protocol Analysis Set

The PPAS is a subset of the FAS. The subjects presenting with at least 1 of the following relevant protocol deviations will be excluded from the PPAS:

- Subjects did not provide a post-dose serology sample

^a Post-final vaccination in each of the immunogenicity parameters is defined as 28 (window, 28–35) days post-final vaccination for subjects 6 months to < 9 years of age, and 21 (window, 21–28) days post-vaccination for subjects ≥ 18 years of age.

^b for which safety data are scheduled to be collected

- Subject did not meet all protocol-specified inclusion criteria or met at least 1 of the protocol-specified exclusion criteria
- Subject did not complete the vaccination schedule
- Subject received a vaccine or dose other than the one that he/she was assigned to receive
- Preparation and/or administration of vaccine was not done as per-protocol
- Subject did not receive vaccine in the proper time window
- Subject did not provide a post-dose serology sample in the proper time window
The proper time window for Group 1 and Group 2 is 28–35 days after final vaccination, and for Group 3, Group 4 and Group 5, the proper time window is 21–28 days post-vaccination.
- Subject received a protocol-prohibited therapy/medication/vaccine that might impact antibody response to the study vaccine
- Any other deviation identified during conduct of the study and judged by the clinical team during data review as having a potential impact on the assessment of immunogenicity

In addition to the reasons listed above, subjects will also be excluded from the PPAS if their post-vaccination serology sample did not produce a valid test result for any antigen.

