5.2.5 Populations Used in Analyses

Baseline and demographic analyses will be performed on all enrolled subjects and/or the analysis sets described above, as appropriate.

The safety analyses will be performed on the Safety Analysis Set.

The immunogenicity analyses will be performed on both the FAS and PPAS.

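### Does the Full Analysis Set leave open whether immunogenicity in randomised Groups 3 and 4 is reported by vaccine assigned or vaccine received?

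*SAP*

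**What the plan says.** Adults 18 to < 65 years are randomised between Fluzone Quadrivalent (Group 3) and Flublok Quadrivalent (Group 4), 60 planned in each. SAP 3.1 words each group by assignment, for example "Group 4: Adults 18 to < 65 years of age assigned to receive a 0.5-mL dose of Flublok Quadrivalent vaccine".

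For immunogenicity, SAP 5.1.3.2 states that "Data will be summarized and presented for each age group". Protocol 12.1.3.2 has the same sentence. The Statistical Methods part of the protocol synopsis differs: after naming both immunogenicity analysis sets it says "Data will be summarized and presented for each group".

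The three analysis sets treat a wrong vaccine differently:

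- **Safety Analysis Set** (SAP 5.2.1): "Subjects will have their safety data analyzed after each vaccination according to the vaccine they actually received for that dose".
- **PPAS** (SAP 5.2.3) excludes a subject for this deviation: "Subject received a vaccine or dose other than the one that he/she was assigned to receive".
- **FAS** (SAP 5.2.2) is the "subset of subjects who received at least 1 dose of the study vaccine and have a valid post-vaccination blood sample result" for at least one strain. No grouping rule is given.

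SAP 5.2.5 then says: "The immunogenicity analyses will be performed on both the FAS and PPAS". Protocol 6.6 lists compliance measures so that "any non-compliance is documented so that it can be accounted for in the data analyses".

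**The concern.** Groups 3 and 4 are the trial's only randomised pair, and one age band covers both. Read literally, the SAP's presentation unit cannot separate them, and so cannot say where to put a subject who was assigned one vaccine and given the other. The safety set has an explicit rule and the per-protocol set drops the subject. The FAS keeps the subject without saying in which column.

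The plan recognises that such errors can happen: receipt of the wrong vaccine is a listed PPAS exclusion, and an error in vaccine administration is an example of a protocol deviation in Protocol 5.2.10. The trial is open-label, so a rule not fixed in advance could be chosen with vaccine and titers in view. At stake are the FAS titers, seroprotection rates and seroconversion rates for both vaccines.

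**Working it through.** **Step 1. Is a rule stated?** In the documents, the as-received rule appears only for safety: under the safety heading of the synopsis, in Protocol 12.2.1 and in SAP 5.2.1. Neither FAS definition (Protocol 12.2.2, SAP 5.2.2) names assigned or received. So no explicit rule exists for FAS immunogenicity.

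**Step 2. What does the plan imply?**

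| Place | Cue | Points to |
|---|---|---|
| Synopsis, immunogenicity paragraph | FAS and PPAS results shown by group | the five defined groups |
| Synopsis, Protocol 5.1.1, SAP 3.1 | each group defined by the vaccine assigned | assigned |
| SAP 3.1, Groups 1, 2 and 5 | age determines the assigned group | assigned |
| SAP 5.2.1 | as-received written for safety data only | not carried over to immunogenicity |
| SAP 5.1.3.1 | safety tabulated by treatment group, as received | safety only |
| Protocol 12.5, SAP 5.5 | groups described by the vaccine to be given | enrolment plan, neutral |

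The first two rows together give grouping by assignment. The age-group wording is loose, since pooling two different vaccines in one row would not meet the objective of describing each vaccine.

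**Step 3. How large could the difference be?** The plan has no figure of its own to reproduce, beyond group sizes that add up: 30 + 30 + 60 + 60 + 60 = 240. The documents give no error rate. Assume k = 1 to 3 of the 60 Group 3 subjects receive the Group 4 vaccine. Intervals are Clopper-Pearson 95%, the SAP's method.

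*Group 3 rate near 50%.* As assigned: 30/60 = 50.0% (36.8 to 63.2).

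- k = 1, as received: 30/59 = 50.8% or 29/59 = 49.2%, a shift of 0.8 points.
- k = 3, as received: 30/57 = 52.6% or 27/57 = 47.4%, a shift of 2.6 points.

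*Difference between groups.* The plan does not specify this contrast, but a reader may form it. Assume 30/60 in Group 3 and 36/60 = 60.0% in Group 4, a difference of 10.0 points as assigned.

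- k = 1, as received: 36/61 − 30/59 = 8.2 points, to 37/61 − 29/59 = 11.5 points.
- k = 3, as received: 36/63 − 30/57 = 4.5 points, to 39/63 − 27/57 = 14.5 points.

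For scale, the normal-approximation half-width of the difference is 1.96 × √(0.50 × 0.50/60 + 0.60 × 0.40/60) = 1.96 × 0.0904 = 17.7 points. The largest movement is 10.0 − 4.5 = 5.5 points.

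*Geometric mean titer.* If titers under the two vaccines differ by a factor r, the as-assigned Group 3 mean differs from the as-received one by r^(k/60):

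| r (assumed) | k = 1 | k = 3 |
|---|---|---|
| 1.5 | 1.007 (0.7%) | 1.020 (2.0%) |
| 3 | 1.018 (1.8%) | 1.056 (5.6%) |

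*Extreme case.* If three misallocated subjects were also the only Group 3 non-responders, the rate would be 57/60 = 95.0% (86.1 to 99.0) as assigned and 57/57 = 100% (93.7 to 100) as received. The lower limit moves 93.7 − 86.1 = 7.6 points. This needs the three subjects given the vaccine with 3 times the antigen (45 µg against 15 µg per strain) to be the only ones who fail to respond.

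With k = 0 the two rules give identical tables.

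**The case for a change.** The best case for acting is that the reading in Step 2 is an inference. The word group does not settle the matter by itself, because safety is tabulated by treatment group yet analysed as received. The objective is to describe the immunogenicity of each vaccine, which could be taken to favour the vaccine actually given. Two programmers could therefore produce different FAS tables. With three misallocations and the assumed rates, the descriptive difference could lie anywhere from 4.5 to 14.5 points. A single sentence would close the question before anyone sees titers in an open-label trial.

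It is true that no sentence states the rule and that the age-group wording does not separate the two randomised groups. The claim that the cues conflict does not stand. The treatment-group wording sits in a safety section with its own express as-received rule, so it says nothing about immunogenicity. Limiting that rule to safety leaves the assignment-based group definitions to govern elsewhere.

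The worry about a choice made with results in view is limited. The PPAS is reported alongside the FAS and removes wrong-vaccine subjects. Protocol 12.1 and SAP 5.1 require the number and description of protocol deviations to be reported. A reader would thus see both the deviation and an analysis unaffected by it. There are also controls on the error itself: the response system names the vaccine and staff confirm it (Protocol 6.5), and monitors check administered doses against that system (Protocol 6.3.2.3).

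**Conclusion.** No change is needed. This is a detail that analysts would fill sensibly, together with a loose phrase. The synopsis and the group definitions lead to five columns by vaccine assigned; the age-group sentence does not show an intention to pool Groups 3 and 4.

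The effect is nil unless a Group 3 or Group 4 subject receives the other vaccine. For 1 to 3 such subjects out of 60, it is 0.8 to 2.6 points on a rate near 50%, at most about a fifth of the 13.2-point half-width of that interval (2.6/13.2 = 0.20). For the Group 3 geometric mean titer it is 0.7% to 5.6%. These sizes rest on assumed misallocation counts, an assumed rate near 50%, and an assumed 1.5- to 3-fold ratio between the vaccines' titers. The 7.6-point case is a constructed extreme and should not set the weight of the point.

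All analyses are descriptive, no hypothesis is tested, and no comparison of Group 3 with Group 4 is specified. No decision depends on the choice, and following the plan as written does not give a wrong result.

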2.1.2 Immunogenicity

To describe the immunogenicity of the 2018–2019 formulation of Fluzone Quadrivalent vaccine in children 6 to < 36 months of age and 3 to < 9 years of age, and in adults 18 to < 65 years of age, the immunogenicity of the 2018–2019 formulation of Flublok Quadrivalent vaccine in adults 18 to < 65 years of age, and the immunogenicity of the 2018–2019 formulation of Fluzone High-Dose vaccine in adults ≥ 65 years of age.

The endpoints for the observational immunogenicity objective are presented in [Section 9.3.2.1](#).

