6.5 Randomization and Allocation Procedures

On the day of enrollment, subjects who meet all inclusion criteria and no exclusion criteria will be assigned to 1 of 5 vaccine groups (6 to < 36 months of age, Fluzone Quadrivalent vaccine [Group 1], 3 to < 9 years of age, Fluzone Quadrivalent vaccine [Group 2], 18 to < 65 years of age,

Fluzone Quadrivalent vaccine [Group 3], 18 to < 65 years of age, Flublok Quadrivalent vaccine [Group 4], or ≥ 65 years of age, Fluzone High-Dose vaccine [Group 5]); see [Section 6](#) for details regarding the vaccine to be administered to each group. Site staff will connect to the IRT system, enter the identification and security information, and confirm a minimal amount of data (including the number of doses) in response to IRT system prompts. The IRT system will then provide the subject number and vaccine and dose to be administered based on subject’s age and have the site staff confirm it. Subjects 18 to < 65 years of age will be randomly assigned to either Group 3 or Group 4. The full detailed procedures for using the IRT system are described in the Operating Guidelines. If the subject is not eligible to participate in the study, information will only be recorded on the subject recruitment log.

Subject numbers that are assigned by the IRT system will consist of a 12-digit string (a 3-digit country code, 4 digit study center identifier and a 5-digit subject identifier connected by “-”). For example, Subject 8400001-00001 is the first subject enrolled in center number 1 in the United States (840 being the US country code). Subject numbers should not be reassigned for any reason. The randomization codes will be kept securely in the IRT.

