5.1.3.1 Safety

All analyses will be descriptive; no hypotheses will be tested.

The safety analysis will report the occurrence of solicited reactions and the incidence of unsolicited AEs between Visit 1 and Visit 2 (or between Visit 1 and Visit 3 for those subjects receiving 2 doses).

The number of subjects with documented safety will be used as denominator for the frequencies.

- For solicited reactions, the denominator will be the total number of subjects who have non-missing data for the endpoint considered
- For unsolicited AEs, the denominator will be the total number of subjects who were vaccinated with the dose analyzed

The safety tables will be produced using a subject approach; i.e., number of subjects who experienced at least 1 safety event during a considered period.

The 2-sided 95% CIs for the percentages will be calculated using the exact binomial method (Clopper-Pearson method).

Solicited reactions

The solicited injection site reactions and the solicited systemic reactions will be presented separately (except in summary tables).

Solicited reactions will be presented according to their nature (Medical Dictionary for Regulatory Activities [MedDRA, the latest version at database lock] PT), intensity (Grade 1, 2, or 3), time to onset, and number of days of occurrence.

Unsolicited AEs

Unsolicited AEs included in the analysis will be summarized in the safety overview and analyzed according to their nature (MedDRA [the latest version at database lock] system organ class [SOC] and PT classification) and relationship to the vaccination.

Injection Site Reactions

For each treatment group, the number and percentage of subjects experiencing any injection site reaction after injection will be calculated.

The description of injection site reactions will be presented according to:

- Solicited injection site reactions
All solicited injection site reactions that occur each day within 7 days after injection will be analyzed.
- Unsolicited injection site reactions
All unsolicited injection site reactions between Visit 1 and Visit 2 (or between Visit 1 and Visit 3 for those subjects receiving 2 doses) will be described according to the type of events.

Systemic Events and Reactions

For each treatment group, the number and percentage of subjects experiencing any unsolicited immediate systemic event in the 20 minutes after injection will be calculated.

In addition, the description of systemic events will be structured according to:

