- Solicited systemic reactions
- All solicited systemic reactions that occur each day within 7 days after injection will be analyzed.
- Unsolicited systemic events
All unsolicited systemic events between Visit 1 and Visit 2 (or between Visit 1 and Visit 3 for those subjects receiving 2 doses) will be described according to the type of events.

Serious Adverse Events

The number and percentage of subjects with SAEs after vaccination between Visit 1 and Visit 2 (or between Visit 1 and Visit 3 for those subjects receiving 2 doses) in each treatment group will be calculated by outcome, seriousness, and relationship to vaccination.

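### Does presenting immunogenicity by age group merge the two randomised adult vaccines?

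*SAP*

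**What the plan says.** The sentence that sets the unit of presentation for immunogenicity, in SAP section 5.1.3.2, is "Data will be summarized and presented for each age group". Protocol section 12.1.3.2 has the same words. The Statistical Methods part of the protocol synopsis differs by one word: "Data will be summarized and presented for each group".

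The SAP uses another label for safety. In section 5.1.3.1, injection site reactions are introduced by "For each treatment group, the number and percentage of subjects experiencing any injection site reaction after injection will be calculated", and SAEs are to be counted "in each treatment group will be calculated by outcome, seriousness, and relationship to vaccination". The SAP defines neither age group nor treatment group as a term.

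The design in SAP section 3.1 lists five numbered groups, two of which share an age range. One of the two is set out as "Group 3: Adults 18 to < 65 years of age assigned to receive a 0.5-mL dose of Fluzone Quadrivalent vaccine (60 subjects planned"). Group 4 has the same age range, injection volume and planned size, but its subjects are given Flublok Quadrivalent instead.

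Protocol section 6.5 says that eligible subjects "will be assigned to 1 of 5 vaccine groups". The immunogenicity objective (protocol section 2.1.2, repeated in SAP section 2) treats each vaccine as a separate item, including "the immunogenicity of the 2018–2019 formulation of Flublok Quadrivalent vaccine in adults 18 to < 65 years of age".

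**The concern.** Age cannot separate Groups 3 and 4. They cover the same range, subjects are randomised between them, and they differ by vaccine. Protocol section 6 gives 15 µg of HA per antigen for Fluzone Quadrivalent and 45 µg for Flublok Quadrivalent, a ratio of 45/15 = 3. An analyst who built the tables strictly by age range would report one set of titers, ratios and rates for adults aged 18 to under 65, averaged over both products. That would not answer an objective stated for each vaccine.

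The worry is sharper because the loose phrase sits in the two sections that specify the immunogenicity analysis. The better wording appears only in the protocol synopsis, and the SAP has no synopsis.

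**Working it through.** **Group sizes (SAP section 3.1; total in SAP section 5.5).** 30 + 30 + 60 + 60 + 60 = 240, which reproduces the stated planned enrolment.

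**Columns under each reading of the phrase.**

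| Reading | Columns | Planned n |
|---|---|---|
| Numbered groups 1 to 5 | 5 | 30, 30, 60, 60, 60 |
| Four age ranges, vaccine ignored | 4 | 30, 30, 120, 60 |
| Adult randomisation strata used as age groups, vaccine ignored | 5 | 30, 30, about 60, about 60, 60 |

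In the second row the mixed column holds 60 + 60 = 120 subjects, and 120/240 = 50%. In the third row, SAP section 3.1 stratifies adults about equally into 18 to under 50 and 50 to under 65, so each stratum has about 120 × 0.5 = 60 subjects, again across both vaccines.

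**What would be lost if the second reading were followed.** The documents give no expected response rates, so the rates here are assumptions. With equal arms, the combined rate is the mean of the two, so it lies half the true difference away from each. For assumed differences of 0 to 20 percentage points, it misses each vaccine by 0 to 10 points. At the upper end, take 36/60 = 60% and 48/60 = 80%. The Clopper-Pearson limits are the 2.5% quantile of Beta(x, n − x + 1) and the 97.5% quantile of Beta(x + 1, n − x):

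- 36/60: 60% (95% CI 46.5 to 72.4)
- 48/60: 80% (95% CI 67.7 to 89.2)
- combined, (36 + 48)/120 = 84/120: 70% (95% CI 61.0 to 78.0)

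The literal reading would therefore matter if anyone applied it. The question is whether the plan leaves that open.

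**The phrase against the rest of the text.**

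1. *Objectives (protocol 2.1.2, SAP 2).* Fluzone Quadrivalent and Flublok Quadrivalent in adults aged 18 to under 65 are separate items. Rows two and three of the table cannot meet them; row one can.
2. *Group definitions (protocol 5.1.1 and 6.5, SAP 3.1).* There are five groups, each with its own vaccine and planned size.
3. *Synopsis.* It has the same sentence without the word age.
4. *Per-protocol set (SAP 5.2.3).* The blood sampling window is set by group number, with Groups 3, 4 and 5 named individually, and subjects given a vaccine other than the one assigned are excluded. One of the two sets used for immunogenicity is thus built on numbered group and assigned vaccine.
5. *Adult strata (SAP 3.1).* The documents call these subgroups, use them only for enrolment and allocation, and specify no immunogenicity summary for them. The third reading has no other support.

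All five points agree with row one, and none supports a column that mixes vaccines.

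**The case for a change.** The strongest case for acting is that a SAP should state its own rule. Section 5.1.3.2 holds the only sentence in the SAP that fixes how immunogenicity results are grouped. Table 5.1 names no grouping, the Full Analysis Set definition does not mention it, and an analyst who checks protocol section 12.1.3.2 meets the same phrase again. The correction is one phrase in each document, and protocol section 5.4 allows administrative changes to the protocol without IRB approval, on notification.

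The description of the text stands: the wording is inconsistent, and it sits in the operative sections. The inference does not. The phrase also fits the intended reading, with each vaccine shown within its age range, so it is loose rather than contradictory. To arrive at a combined column, an analyst would have to set aside the objectives, the group list and the per-protocol rules in the same SAP. A cheap edit still needs something to gain, and this one would produce only the five-group tables already planned.

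**Conclusion.** This is a clerical slip with no practical consequence. In SAP section 5.1.3.2 and protocol section 12.1.3.2, age group is a loose label for Groups 1 to 5. The literal reading would affect one column holding 120 of 240 planned subjects, but nothing else in either document supports it and several sections exclude it.

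Every analysis is descriptive, with no hypothesis test and no power calculation, so error rates, sample size and data collection do not turn on the phrase. The conclusion assumes that whoever programs the tables reads the SAP as a whole, and that the table layouts, which are not in the two documents, follow the five groups. Both are ordinary expectations here. The assumed response rates above only illustrate the stake and do not bear on the conclusion.
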